## **9.2.3 Overview of the family linkage**

### **9.2.3.1 Neurodevelopmental disorders, including autism**

[figure not shown]
For the purpose of the evaluation of NDD, including ASD, Figure 3 illustrates the registry linkage of the study participants, the paternal exposure period (3-months prior to LMP2 date, for further details please see footnote 10), follow-up period for the offspring (from birth to maximum 12 years of age for Denmark and Sweden and 10 years of age for Norway), and the look back periods for confounders for each linked family member (mother: 12 months prior to delivery, father: 12 months prior to LMP2 date).

---

 Non-live births are not included because a diagnosis of NDD cannot be made

 A patient is considered continuously enrolled in a specific time period if that patient had a contact with healthcare services (such as drug prescription or hospitalisation) prior to that period and if emigration or death were not notified after this contact.

[figure not shown]
 A patient is considered continuously enrolled in a specific time period if that patient had a contact with healthcare services (such as drug prescription or hospitalisation) prior to that period and if emigration or death were not notified after this contact.

[figure not shown]

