### 9.3.1 Exposure definition and measures

Within the AEDs, the primary exposure of interest is the dispensation of valproate. Brand names and generics of all forms of valproate salts will be considered (sodium valproate, valproic acid, valproate semisodium and valpromide) and summarized under the term “valproate”. Valproate will be identified using Anatomical Therapeutic Chemical (ATC) code N03AG01.

*Drug exposure of the offspring is based on the use of AEDs by the father during a risk window prior to conception. Since the spermatogenic cycle is approximately 2.5 months, the risk window considered here is three months prior to conception. Further details are presented in section 9.3.1.3*

As reported in section 9.7.3.2, in the primary analysis, paternal exposure to valproate (monotherapy) will be compared to paternal exposure to lamotrigine or levetiracetam (composite monotherapy). These drugs are generally associated with lower risk of teratogenicity for the offspring of women, however it is unknown whether the effect is the same in men. Lamotrigine and levetiracetam will be identified using ATC codes N03AX09 and N03AX14, respectively. Since polytherapy is indicated for medically refractory epilepsy (14), in order to avoid the risk of disease severity bias associated to polytherapy, evaluation of AED exposure according to monotherapy is preferred for comparative analyses. In this section, definitions of monotherapy and polytherapy are only discussed for AEDs. Co-medications (other than AEDs) are defined in section 9.3.3 (Potential confounding variables). Monotherapy is defined as the exposure to a single AED, whilst polytherapy is defined as any combination of AEDs (including valproate among the exposed and excluding valproate among the unexposed), simultaneously or in sequence, within the 3-months risk window. For example, switching to or switching from an AED other than valproate, lamotrigine or levetiracetam, will be considered as polytherapy, and the offspring of these fathers will be excluded from the comparative analyses. This is because a washout period is not possible in clinical practice since subjects may not be unexposed for seizure control. Including people who were exposed to more drugs of the same class, in the period of interest, could lead to uncertainty in defining which drug is associated with the outcome.

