**Figure 6: Treatment exposure windows, NDD including ASD; CM for Sweden only**

 In order to account for potential dispensations that can have led to an intake during the 3 months look-back period under investigation, all dispensations that are recorded in the 6 months before conception that gave rise to an AED intake during the 3 months prior to conception will be considered. Because information on the exact number of days supplied is not available, patients' drug use periods will be calculated using the defined daily doses (DDD) metric as defined by the World Health Organization. For each prescription the total number of DDDs will be translated into the number of days in which the patient was treated, counting 1 DDD per day and distributing all available DDDs to the days of follow-up and allowing for the use of accumulated DDDs over time.

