### 9.3.1.3 Classification of exposure

Particular care will be taken in the definition and classification of paternal exposure. Person-time exposed will be classified to take into account intensity of drug exposure during the 3-months pre-conception risk window using the longitudinal K-means clustering (R package kml) algorithm (15). This method allows for a more precise description of exposure of fathers to drugs and allows profiles to be distinguished improving evaluation of effects of drugs on outcomes. In summary the following steps apply:

- To quantify drug exposure, for each individual, prescription data will be transformed into the standard units of measurement of the World Health Organization (WHO): the Defined Daily Dose (DDD) (Figure 8). The duration of treatment and dates of exposure

 See footnote 10

will be estimated assuming individuals are exposed to one DDD per day and using information on number of units and dates of prescriptions, where available. For the father, drug prescribed and dispensed three months before the LMP2 date (including the LMP2 date) will be taken into account. A validation of the assumption that individuals are exposed to one DDD per day will be provided as a sensitivity analysis (section 9.7.5).

- After super imposing length of exposure onto the spermatogenic risk window, exposure data will be individually transformed into number of DDDs (Figure 8) dispensed during every 14 day interval within the 3-months exposure period. This way, the cumulative drug exposure of each father will be evaluated at several time points, and the exposure data will become longitudinal which will allow drawing individual trajectories of exposure through the pre-conception period. Data will be censored at the LMP2 date.

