### 9.9.2 Study analysis limitations

- Restriction to monotherapy could lower the generalizability of the results due to differences in real life clinical practice. One study found that approximately half of the population become seizure free on their first drug (65), while others need to switch or add additional AEDs. The selection of the cohort for analysis for the primary objective based on paternal valproate or lamotrigine/levetiracetam monotherapy use could potentially result in a small population, and therefore could be underpowered if the sample size falls below that required to detect the desired HR of interest. In the present study, patients who are on AED polytherapy are excluded from the primary analysis. To understand the population of AED polytherapy users, descriptive analysis will be conducted as an exploratory objective. Moreover, during the 3 months prior to LMP2, a father can be exposed to more than one AED in a sequence of monotherapies, that is an exposure to multiple drugs in the period at study, a polytherapy. For this reason, switchers are considered being in AED polytherapy treatment, therefore excluded from the comparative analyses. However, the frequency of switchers will be described.
- It is expected that few offspring will be both paternally and maternally exposed to AEDs, however there will likely be some. Offspring who fall into this category will be excluded in the primary comparative analysis. However, the descriptive analyses of the overall cohort will inform on the understanding of the characteristics of these offspring.

- The exposure window that affects the outcomes of the study could be shorter than the complete 3 months spermatogenic cycle. If so, the methodology used to assess paternal exposure may be able to examine the effect of proximity to conception, in that only selected clusters of paternal exposure can be evaluated. However, this restriction could result in very small sample size. Therefore, the rates of NDD could be under-estimated and the HR estimates of NDD could be biased towards the null.
- It is known that the exposure of AEDs and other medications during breastfeeding is associated with the outcomes of interest. Failing to account for exposure during breastfeeding could lead residual confounding. Breastfeeding data is only available for Denmark and only after 2012.

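### Section 9.3.1.3 and footnote 10 give different look-backs for paternal dispensings (3 versus 6 months); read literally, 9.3.1.3 misses carry-in supply and keeps some switchers in the monotherapy arms

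*Protocol*

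**What the plan says.** Two places in the protocol state which of the father's dispensings count.

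- **Footnote 10** (9.3.1.1, attached to the father's 3-month window) counts "all dispensations that are recorded in the 6 months before conception that gave rise to an AED intake during the 3 months prior to conception". It converts supply to days by "counting 1 DDD per day and distributing all available DDDs to the days of follow-up and allowing for the use of accumulated DDDs over time". Footnote 11 applies the same rule to CM, and 9.2.3.1 describes the exposure period as "3-months prior to LMP2 date, for further details please see footnote 10".
- **Section 9.3.1.3**, which 9.3.1 names as the place for further details, says: "For the father, drug prescribed and dispensed three months before the LMP2 date (including the LMP2 date) will be taken into account". That bullet has no carry-in clause and no reference to footnote 10. The next bullet begins "After super imposing length of exposure onto the spermatogenic risk window" and then counts DDDs by 14-day interval.

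The classification that depends on this is set elsewhere. Section 9.3.1 defines polytherapy as any combination of AEDs, "simultaneously or in sequence, within the 3-months risk window". Section 9.9.2 says "switchers are considered being in AED polytherapy treatment, therefore excluded from the comparative analyses". Section 9.7.3 repeats the exclusion for switches to or from an AED outside the three study drugs.

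**The concern.** The split between monotherapy and switching defines both arms of every comparative analysis. If the look-back stops at the edge of the window, a pack filled just before it is invisible even though the father was taking it inside the window. A man who finished such a valproate pack and then started lamotrigine is a sequential user under 9.3.1 and 9.9.2 and should be excluded. Under the 9.3.1.3 wording he looks like a lamotrigine monotherapy user and enters the reference group. If valproate raises risk, that brings exposed offspring into the comparator and draws the HR towards 1. In a safety study this is the direction that can hide harm.

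The intensity measures are also affected. A steady user would seem to start part-way through the window. That imitates a rising trajectory in the k-means clustering and lowers the cumulative DDD total used in sensitivity analysis 10.

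**Working it through.** The protocol gives no figure for this point, so there is none to reproduce.

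**One father under both rules.** Suppose 90 days of valproate are dispensed at day −150 and lamotrigine at day −60, counted from LMP2.
- Footnote 10: the valproate fill is within 6 months and its supply lasts until about day −60, so it covers roughly the first 30 days of the window. He used two AEDs in sequence and is excluded.
- 9.3.1.3: the only fill in the last 3 months is lamotrigine. He is lamotrigine monotherapy and is in the reference group.

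**Share of in-window switchers missed by the 3-month rule.** Inputs:
- W = 90 days, for the 3-month window.
- L = days supplied per fill. The protocol does not give it, so a range is assumed.
- One switch per man, uniform over the window.

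The old drug is missed when its last fill precedes the window.

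- Switch at a random point in a supply: share = L/(2W) for L ≤ W, otherwise 1 − W/(2L). A simulation of 2,000,000 switches agrees.
- Switch when the supply runs out: share = min(1, L/W).

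| L (days) | Random point | At run-out |
|---|---|---|
| 30 | 30/180 = 17% | 30/90 = 33% |
| 60 | 60/180 = 33% | 60/90 = 67% |
| 90 | 90/180 = 50% | 90/90 = 100% |
| 120 | 1 − 90/240 = 62.5% | 100% |
| 180 | 1 − 90/360 = 75% | 100% |

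A majority is missed only if L exceeds 90 days (random point) or 45 days (run-out).

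**The footnote 10 rule on the same model** (about 180 days of dispensings): nothing is missed for L up to 90 days in either case. At L = 100 it misses 0.6% (random point) or 11% (run-out), and at L = 120 it misses 4% or 33%.

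**Effect on the HR.** If a fraction f of the reference group was in fact exposed to valproate and the true HR is 2.0, the reference hazard becomes (1 − f) + 2f = 1 + f, and the observed HR is about 2/(1 + f). For f = 5% this is 2/1.05 = 1.90, and for f = 10% it is 2/1.10 = 1.82. Both values of f are illustrative.

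**Continuous users.** With fills every L days at a random phase (L ≤ W), the first in-window fill comes on average L/2 days after the window opens. The 3-month rule therefore leaves about 15, 30 or 45 days falsely uncovered for L = 30, 60 or 90.

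**The case against.** The strongest reply is that 6 months was plainly intended. Footnote 10 states the rule and its reason, footnote 11 and 9.2.3.1 point to it, footnote 14 uses the same logic for teratogens, and the Swedish extraction criterion in 9.2.2 reaches back 192 days. Section 9.3.1.3 introduces its steps as a summary and then lays supply over the window, so the sentence may be loose wording for the intake window. Figure 8, which illustrates the calculation, is not shown in the text available here. This stands as evidence of intent. It does not remove the conflict: 9.3.1 directs the reader to 9.3.1.3, and the sentence there restricts dispensing, not intake.

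Three limits on the harm also stand.
- Only switches from valproate to a comparator put valproate-exposed men into the reference arm. A switch between the two comparators stays within the composite, and a switch to valproate leaves an exposed man in the exposed arm, although he too should be excluded.
- The first Cox model in 9.7.3.2.1, for which the study is powered, ignores the clusters. The trajectory distortion therefore reaches only the interaction model and the cumulative-exposure analysis.
- The number of switchers is not given, so contamination of the reference arm cannot be estimated.

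A reader might infer that most in-window switchers are misclassified. The protocol does not support this, because it gives neither supply length nor switch timing. A reader might also want a 9-month look-back for sensitivity analysis 1, to carry supply into its 6-month window. That goes beyond reconciling the two rules. It may also not be feasible in Sweden, where fathers qualify on AED exposure within 192 days before LMP2.

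**Conclusion.** The protocol contains two incompatible rules for the primary exposure variable, and the one in 9.3.1.3, followed literally, contradicts its own exclusion of switchers. Some in-window switchers would be kept as monotherapy. For assumed supplies of 30 to 90 days the share is 17% to 50% if switches fall at random within a supply, and 33% to 100% if they fall at run-out. These are shares of switchers, not of the cohort. They rest on an assumed supply length, one uniformly timed switch and a 90-day window. The bias in the HR is towards 1 if valproate raises risk, and its size is unknown.

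The protocol does not show that the 3-month rule was the one applied. If the footnote 10 rule was programmed, no result changes and the defect is confined to the text.

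**What to change.** Replace the sentence in 9.3.1.3 with the footnote 10 rule: count AED dispensings in the 6 months before LMP2 whose supply reaches into the 3-month window. State that it applies alike to the study drugs, to every other AED used to test for monotherapy or switching, and to the DDD trajectories behind the clusters and the cumulative measure. Confirm that this rule was programmed in Denmark, Sweden and Norway, including the Norwegian re-run listed in the milestones.

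The text change costs one sentence. If a country used the 3-month rule, its exposure step and the comparative and pooled analyses that follow from it need to be re-run.

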- In this study, clusters of fathers with homogenous trajectories of drug intake during the assessment period will be identified, using the number of DDDs in every 14 days interval and grouping fathers with similar “trajectories” of this metric over time. Since it will be assumed that treated fathers will be exposed to 1 WHO DDD per day, the number of DDDs in each 14-days interval also coincides with the number of days covered in the same period (e.g. 10 DDDs = 10 days covered in a specific 14-days interval). The longitudinal K-means clustering algorithm will be applied to create K clusters with homogenous trajectories, as empirically driven by the data. No assumption about the number of clusters is made prior to running the algorithm. Mean DDD trajectories will be plotted for each cluster and shape described. It is anticipated that several clusters of exposed fathers will be identified with homogenous trajectories of exposure during the 3-months risk window. For example, Cluster A = low constant exposure, Cluster B = decreasing exposure, Cluster C = moderate constant exposure, Cluster D = increasing exposure and Cluster E = high constant exposure.

The K-means is a novel method applied in studies investigating medication safety during pregnancy as it can model complex real-world exposures. This method proposed by Hurault-Delarue et al.(15) allows drug exposure during pregnancy to be modelled in a flexible way accounting for treatment intensity and evolution overtime. This methodology attempts to overcome some of the limitations associated with defining exposure using, for example binary classification (ever, never use) or the ‘Intention To Treat’ approach where dose is defined at one time point (e.g conception, or start of 3 months pre-conception period) since AED treatment may be modified if planning for,(or during) pregnancy.

In particular, K-means has been used to identify trajectories of higher or lower medication exposure in studies investigating the effects of maternal exposure to medication during or after pregnancy on infant outcomes, with data from secondary databases (such as electronic health records, prescription orders or dispensation information) (16). The application of this methodology for assessing paternal exposure in the population of this study is novel, albeit follows the same principles.

- Descriptive statistics will summarise distribution of exposure to each AED within each cluster.

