$$\sum_{i=1}^n \left( \frac{\sum_{j=1}^{k-1} \text{days} (\text{prescription}_{j+1} - \text{prescription}_j) * \text{WHO DDD}}{n. \text{pkg in prescription}_j * n. \text{dosage unit in each pkg}} \right) / n$$

where n is the number of patients and k is the number of prescriptions per patient.

Under the assumption of perfect compliance of each patient, if the Ratio for the overall population is between 0.8 and 1.2 then the WHO DDD is a good approximation of the reality; the more the ratio departs from the good approximation range the more the real daily dose prescribed diverge from the WHO defined daily dose. It is expected to have a good approximation to the reality for patients with the epilepsy indication for AEDs.

This measure will be affected both from the approximation of using the WHO DDD and the compliance of patients to the treatment. The less the compliance, the more the ratio departs from good approximation (0.8-1.2). Since the dose prescribed is not available, it will not be possible to assess what affected more the results.

Sensitivity analysis 8 will be performed only in the Primary Outcome Cohort for Descriptive Analyses

9. *Narrow case definition for secondary outcome - focus on CM in live births*: Since the population for analysis of the secondary outcome for Sweden is comprised of live births, the distribution of CM observed in this population is likely to reflect functional defects and minor morphological abnormalities, rather than major morphological abnormalities (usually associated with fatal outcome during gestation). A sensitivity analysis will therefore be performed on the corresponding live birth population for Norway and Denmark to describe the corresponding risk and underlying distribution of CM associated with live births.
10. *Continuous measure of cumulative exposure*: Investigate separately the risk of NDD, including ASD, as well as CM, in offspring paternally exposed to monotherapy treatment with valproate, lamotrigine or levetiracetam at the time of conception, using cumulative exposure to treatment. Cumulative exposure will be calculated as the total amount of DDD intake that a father is exposed to over the 3-months time window prior to LMP2 date, i.e. the sum of the DDD in all 14-day intervals as reported in Figure 8.

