  - a. In order to account for potential differences in the association between the cumulative exposure and the outcome at study between different treatments, an interaction term of the continuous variable representing the cumulative exposure and the dichotomous variable representing the valproate or lamotrigine/levetiracetam group will be tested for in each logistic and Cox PH model.
  - b. The cumulative exposure variable will also be categorised empirically according to tertiles of the distribution to represent low, medium and high exposure to each of the three treatment groups separately, since the cumulative exposure pattern may be different for each treatment, plus thresholds cannot be defined a priori as cut-off points are not available by previous literature. For each exposure group (valproate, lamotrigine and levetiracetam) separately, a within-group analysis will be performed to study the dose-response relationship for each outcome by comparing high and medium exposure to treatment against low exposure to treatment as the referent category.
  - c. For each outcome, a pre-defined list of covariates based on final models of primary comparative analyses will be forced into each of the aforementioned logistic and Cox PH model to provide estimates adjusted for relevant confounders. Since the distribution of cumulative exposure and of relevant confounders within each exposure group could differ from those of the other exposure groups, the results from the three within-exposure group analyses for each outcome will not be comparable.
11. *Narrow case definition for primary outcome - NDD*: This sensitivity analysis will use a narrow NDD composite case definition according to the following ICD-10 codes:

Clinical Code Description	ICD-10
Intellectual disability - mild	F70
Intellectual Disability - Moderate	F71

Clinical Code Description	ICD-10
Intellectual Disability -Severe	F72
Intellectual Disability -Profound	F73
Other Intellectual Disability	F78
Unspecified Intellectual Disability	F79
Specific developmental disorders of speech and language	F80
Specific developmental disorders of scholastic skills	F81
Mixed specific developmental disorders	F83
Childhood autism	F84.0
Atypical autism	F84.1
Other childhood disintegrative disorder	F84.3
Asperger syndrome	F84.5
Other pervasive developmental disorders	F84.8
Pervasive developmental disorder, unspecified	F84.9
Other disorders of psychological development	F88
Unspecified disorder of psychological development	F89

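### The 14-day DDD count stops rising at one DDD per day and below that mixes dose with refill timing, so the intensity and dose-response analyses measure coverage and not dose

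*Protocol*

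**What the plan says.** Footnote 10 (Section 9.3.1.1) explains that "information on the exact number of days supplied is not available", so periods of use are built by "counting 1 DDD per day and distributing all available DDDs to the days of follow-up" and "allowing for the use of accumulated DDDs over time". Section 9.3.1.3 repeats that duration and dates "will be estimated assuming individuals are exposed to one DDD per day". It then says that "exposure data will be individually transformed into number of DDDs (Figure 8) dispensed during every 14 day interval". Read alone, that sentence could mean an uncapped quantity, but the next bullet settles the meaning: "the number of DDDs in each 14-days interval also coincides with the number of days covered in the same period".

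Three analyses rest on this count:

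- Sections 9.7.3.2.1 and 9.7.3.2.2 say that the first model ignores intensity. They offer a second model, with an exposure-by-cluster interaction, as the remedy.
- Section 9.7.5, item 10: "Cumulative exposure will be calculated as the total amount of DDD intake that a father is exposed to over the 3-months time window", obtained by summing the 14-day intervals. Item 10a tests its interaction with treatment group.
- Section 9.7.5, item 10b cuts the same total into tertiles, and "a within-group analysis will be performed to study the dose-response relationship for each outcome".

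Item 8 of Section 9.7.5 concedes that individual doses often differ from the DDD. It plans an observed-to-expected duration ratio, with 0.8 to 1.2 taken as good agreement. It also says that dose and compliance cannot be separated in that ratio. No rule changes the exposure variable when the ratio falls outside the range.

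**The concern.** Under the allocation rule a father's intake on any day is at most one DDD. A higher daily dose does not raise the count: the surplus is assigned to later days. A lower daily dose lowers the count only because stock runs out before the next refill, which is also what a gap, a stop or poor adherence looks like. The variable is therefore days covered, but the plan calls it intensity and uses it to study dose-response.

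In a safety study both possible results are open to misreading. A flat gradient may come from a count that has reached its ceiling. A gradient may come from gaps and stopping and not from dose. The trajectories are affected too. Section 9.3.1.3 gives low-constant and moderate-constant clusters as examples. Yet a steady user of half a DDD per day with 30-DDD packs appears as 30 days on and 30 days off, so he can look as if he is increasing or decreasing purely through refill timing.

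**Working it through.** **Inputs from the protocol.** One DDD used per day with surplus carried forward (footnote 10); dispensings in the six months before conception (footnote 10); 14-day intervals and a three-month window (Section 9.3.1.3); valproate DDD of 1.5 g (Figure 8).

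**Assumptions.** Pack sizes of 15 to 100 DDDs, steady dosing and random refill phase. The look-back is 183 days and the window 91 days, or 180 and 90 where stated.

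**1. The plan's own example.** Ten DDDs in an otherwise empty interval give ten covered days. This reproduces.

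**2. Ceiling.** Daily use = min(1, stock). Maximum per interval = 14 × 1 = 14. Maximum per window = 91 × 1 = 91 (90 if three months is taken as 90 days). For valproate the ceiling is reached at 1.5 g per day.

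**3. At or above one DDD per day.**

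| True DDD/day | True total (× 91) | Count |
|---|---|---|
| 1 | 91 | 91 (a few days fewer for some refill phases with 100-DDD packs) |
| 1.25 | 114 | 91 |
| 1.5 | 136.5 | 91 |
| 2 | 182 | 91 |

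The counts at 1.25, 1.5 and 2 DDD per day did not change with any pack size tried.

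**4. Below one DDD per day.** With regular 30- or 90-day refills and a 90-day window, doses of 0.25, 0.5, 0.67 and 0.8 give 22.5, 45, 60.3 and 72. These equal dose × 90, so dose is visible here. With random refill phase at 0.5 DDD per day (true total 0.5 × 91 = 45.5):

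| Assumed pack (DDDs) | 5th to 95th percentile | Share with zero covered days |
|---|---|---|
| 30 | 32 to 59 | 0% |
| 45 | 45 to 46 | 0% |
| 67 | 24 to 67 | 0% |
| 100 | about 0 to 90 | 8 to 9% |

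At 0.33 DDD per day the zero-day share is 0% (30-DDD packs), 1% (45), 18% (60), 24% (67) and about 40% (100).

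**5. Dose and coverage confused (90-day window).** Half a DDD per day throughout gives 0.5 × 90 = 45. One DDD per day stopped after 45 days also gives 45. A father who receives 180 DDDs 180 days before LMP2 and takes two per day finishes after 180 / 2 = 90 days. The rule spreads his supply over 180 days and credits him with 90 covered days in the window, when his true intake there is zero.

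**6. Tertiles.** These use assumed uniform dose distributions, 90-day refills and a 90-day window.

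| Dose range (DDD/day) | Share at ceiling | Rank correlation with true dose | Tertile cuts |
|---|---|---|---|
| 0.2 to 1.0 | 0% | 1.00 | 41.5, 65.6 |
| 0.5 to 1.5 | 51% | 0.93 | 75.4, 90 |
| 0.5 to 2.0 | 65% | 0.85 | 88.4, 90 |
| 1.0 to 2.0 | 100% | undefined | 90, 90 |

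Once more than a third of fathers are at the ceiling, the upper cut lies on it and the high group cannot be ranked by dose. Both cuts coincide only when about two thirds or more are there.

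**The case against.** The strongest reply is that much of this is disclosed. Section 9.3.1.3 says openly that DDDs and covered days are the same number, and describes the clusters as homogeneous for both duration and intensity. Item 8 checks the one-DDD assumption by drug and by epilepsy indication, and admits that dose and compliance are entangled. That stands as disclosure. But item 8 only describes a ratio, and its caveat is not carried into the interaction models or item 10.

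A second reply is that the count is not uninformative, and this also stands. A reader might infer that the analyses cannot see dose at all. That goes too far, because below one DDD per day the total follows dose on average, and exactly so for regular refillers in step 4.

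A reader might also infer that low-dose fathers are routinely classed as unexposed, or that the tertile boundaries collapse. Neither is established. Zero covered days appear in these runs only with long refill intervals: 100 DDDs at 0.5 per day last 200 days. The protocol gives neither pack sizes nor the share of fathers at the ceiling.

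Finally, a refill-based dose has faults of its own. It recodes gaps as lower dose and needs at least two dispensings, and spreading supply to the next refill would erase the gaps that the trajectories are meant to show. This is a fair argument against replacing the present variable. It is not an argument against adding a second one.

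**Conclusion.** The point holds in this form: the count saturates at one DDD per day and below that mixes dose with refill timing, gaps and stopping. The intensity interaction and sensitivity analysis 10 therefore cannot distinguish doses above one DDD per day, or separate dose from coverage. The ceiling follows from the protocol's text alone. The spread below it depends on assumed pack sizes, from 32 to 59 up to about 0 to 90 at 0.5 DDD per day. The overall loss depends on the unknown share of fathers at or above one DDD per day.

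A reader might extend this to the primary result. The documents do not support that: the primary model is dichotomous and fitted irrespective of the clusters, so it does not use this count. Nor does the protocol say that a flat gradient would be taken as evidence against an effect. That is a risk of interpretation, not a stated rule. The change should be made, but it concerns what the secondary models and item 10 can claim, not the main contrast.

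**What to change.** 1. Keep the current variable but call it *days covered* in Sections 9.3.1.3, 9.7.3.2.1, 9.7.3.2.2 and 9.7.5 (item 10). State that its gradient is not interpreted as dose-response.
2. For item 10, and as a supplementary version of each interaction model, add an uncapped average daily dose per father: DDDs dispensed divided by days between dispensings. These are the two quantities already in item 8, where observed over expected duration is days per DDD, so the dose is its reciprocal.
3. Use at least 12 months of dispensing history before LMP2 where available, and only dispensings up to LMP2. Six months is too short: at 100 DDDs and 0.5 per day, refills are 200 days apart, so a 183-day look-back holds fewer than two.
4. Report fathers with a single dispensing separately.

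The cost is programming on data already held. Item 8 is planned only in the primary outcome cohort, so the calculation must be extended to the malformation cohort. The drawback is that refill-based dose mixes dose with adherence. Item 8 already acknowledges this limit for its ratio, and it should be stated beside the results.
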